#### **4.2.8 Treatment Exposure**

Dosing data will be summarized by treatment group for the Safety population using descriptive statistics to include duration of exposure (days). The count and percent of subjects who have total number of dose of 1, 2, 3, 4, 5 or 6 will also be presented.

Duration of exposure is calculated as: date/time of last dose – date/time of first dose, expressed in days with one decimal point.

Dosing information collected will also be presented in a by subject data listing.

### **4.3 Analysis of Efficacy Endpoints**

#### **4.3.1 Primary Efficacy Analysis**

The primary analysis for the study will compare the 28-day all-cause mortality risk between the planned treatment groups in the FAS using a stratified Cochran-Mantel-Haenszel test controlling for the randomization strata site. Sites with low enrollment will be pooled. Pooling criteria has been described in [section 3.5](#). Count and percent of subjects with known status (dead or alive) and also unknown status will be presented. Subjects with unknown mortality status at Mortality Day 28 will have their mortality status imputed as outlined in [Section 3.4](#). For purposes of hypothesis testing, known dead and assumed dead subjects will be grouped together; similarly, known alive and assumed alive will also be grouped together.

A table presenting count and percent of subjects who are known dead, known alive or have unknown status will be also presented for Study days 3, 7, 14, 28, 90, 180, and 360 as well as mortality day 28 by treatment group and overall. The Kaplan-Meier survival estimates will be presented for each time-point although the survival estimate will not be presented for the total column. A stratified (by treatment) log rank test will be performed to assess the difference between treatment groups which will include all available mortality data as of the date of data cut, not just mortality data up to mortality day 28.

Kaplan-Meier plots of survival time will be also provided. Time to death is defined as the time from the first dose to death in days. Subjects without death records will be censored at the last point they were known to be alive.

Additionally, an investigation of the degree of variance reduction resulting from the stratification will be investigated with the use of an un-stratified test (Chi-squared test) of the primary endpoint.

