5.16 Survival Status at Day 28 (+3 day) Visit

Please note that survival status must reflect subject status on or after the 29th calendar day, which is 28 days after the administration of the first dose of the study drug. If subject has died, additional information required includes:

- Date of Death
- Cause of Death (including Death Certificate and autopsy results if available)

5.17 3 Month, 6 Month and 12 Month Follow-Up Visits

Subjects will be contacted to obtain their survival status at 3 months (90 ± 3 Days), 6 months (180 ± 3 Days) and 12 months (360 ± 3 days) post the first dose of study drug. This information can be obtained via telephone or in person. All reasonable efforts must be made to obtain the actual survival status for the subject. At a minimum, there must be 2 documented telephone calls to the subject's last known telephone number and a certified letter sent to their last known address. If a subject cannot be located at 3 months, the same attempts must be made at 6 months and 12 months respectively. Subjects will only be considered lost to follow up if they cannot be located at 12 months post study completion.

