### 3.3 Study Day and Visit Windows

When study results are reported by time point (e.g., Day 3 or Day 28) the observation included at the time point will be based upon the actual date and time the event was recorded. Study Day and Study Hour, as defined below, as well as the Analysis Visit algorithm outlined in [Table 1](#) will be used to determine how to map the observed results to time points. Analysis of Day 28 mortality and time till death will not use these conventions. These mortality analyses will be based upon days since the start of treatment and not these analysis visits as discussed in [Section 3.6.1](#) of this SAP.

Study Hour is calculated for any event for which time is recorded in the CRF. Study Hour is defined as,

$$\text{Study Hour} = \text{Assessment Date and Time} - \text{First Dose Date and Start Time.}$$

Study Hour is reported as XX.Y where XX is the hours between the events and Y is the decimal representation of the remainder minutes (e.g. 2 hours and 30 minutes is recorded as 2.5 and not 2.3). Study Hour may be negative for events that occur prior to treatment.

Study Day is defined as the days between the event and the start of treatment as follows:

Events that occur on or after 1 st Dose:	Assessment Date – First Dose Date + 1
Events that occur before 1 st Dose:	Assessment Date – First Dose Date.

Study Day as defined above and the study day defined in the protocol may not agree due to naming conventions and the fact that study day defined in the protocol is defined based upon hours from the start of treatment. For example, if the first dose occurs at 11:00 pm and vital signs are taken at 1:30 am the next day, the Study Day would be 2 for these vital signs and Study Hour would be 2.5. For reporting purposes, Study Day and Study Hour are used to assign the assessment to an Analysis Visit. In this example the vital signs would be reported on Analysis Visit = Day 1.

Analysis Visit, AVISIT, is defined based upon Study Hour (SH) when available and will occur between -24 and 164 hours. When Study Hour is unavailable or not within this range Analysis Visit is defined based upon Study Day (SD). See [Table 1](#) below for the derivation of Analysis Visit.

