### **3.6.3 Day 28 Event Free and Alive Analysis**

Event free and alive endpoints at the end of the study will be summarized with continuous variable descriptive statistics. Differences between treatment arms will be subjected to testing. These tests will look for a difference in the distribution of the number of event free and alive days between treatment arms. The test used will be a stratified Wilcoxon test (van Elteren test). The study has not been powered to test these differences and multiplicity adjustments for these tests will not be utilized. The 5 event free and alive endpoints include,

1. Shock free and alive days (secondary endpoint)
2. Ventilator free and alive days (secondary endpoint)
3. Dialysis free and alive days (secondary endpoint)
4. ICU free and alive days (tertiary endpoint)
5. Hospitalization free and alive days (tertiary endpoint)

The number of event free and alive days is defined as:

$$\text{Alive Days} - \text{Event days}$$

---

 The definition of Study Day can cause confusion concerning Day 28 mortality status. Twenty-eight days after the start of treatment is Study Day 29 and so Day 28 mortality status is determined by evaluating if a subject died on or before Study Day 29.

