#### **4.3.2 Secondary Efficacy Analyses**

##### **4.3.2.1 All-cause Mortality at Month 3**

The Kaplan-Meier method will be used to estimate the survival rate at month 3 (study day 87). Kaplan-Meier plots of survival time will be also provided. All long term follow up data at the time of analyses will be used to obtain month 3 Kaplan-Meier estimates. Subjects whose status is alive, or unknown will be censored at the last available date that the subject was known to be alive.

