### **4.3.3 Additional Analyses**

#### **4.3.3.1 All - Cause Mortality for Month 6 and 12**

All-cause mortality at month 6 (study day 177) and 12 (study day 350) will be analyzed in a similar way as that at month 3.

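### SAP 4.3.1.1 stratifies a supportive log-rank test by treatment, so it cannot be computed, and the SAP's long-term mortality days disagree, with day 350 fitting no stated rule

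*SAP*

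**What the plan says.** **Log-rank test.** The survival paragraph placed under SAP 4.3.1.1 reads: "A stratified (by treatment) log rank test will be performed to assess the difference between treatment groups which will include all available mortality data". Other sections describe the stratification differently. SAP 3.6.2 (long-term mortality) and SAP 3.6.5 (time to death over all follow-up, a sensitivity analysis) both stratify by pooled site. SAP 3.5 stratifies tests of the primary and secondary endpoints by site. Protocol 10.5.2 plans a stratified log-rank test for survival time.

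**Time points.** The SAP 4.3.1.1 status table covers "Study days 3, 7, 14, 28, 90, 180, and 360 as well as mortality day 28", and "The Kaplan-Meier survival estimates will be presented for each time-point". SAP 4.3.2.1 says "The Kaplan-Meier method will be used to estimate the survival rate at month 3 (study day 87", and SAP 4.3.3.1 refers to "All-cause mortality at month 6 (study day 177) and 12 (study day 350". Protocol 5.17 schedules the contacts at 90 ± 3 days for month 3, and then at "6 months (180 ± 3 Days) and 12 months (360 ± 3 days) post the first dose of study drug".

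**Day axis.** SAP 3.3 defines Study Day on or after first dose as date minus first-dose date plus 1. It then exempts the mortality analyses: "Analysis of Day 28 mortality and time till death will not use these conventions"; they count days since the start of treatment. SAP 4.3.1.1 likewise measures time to death from first dose. Yet SAP 4.3.1.1, 4.3.2.1 and 4.3.3.1 all label their time points as study days.

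**The concern.** A prespecified between-arm test is defined so that it has no value, and it contradicts the sections that define the same kind of test correctly. Separately, the SAP gives two sets of days for months 3, 6 and 12 and no rule for which is reported. The 12-month value in 4.3.3.1 would be read before any scheduled 12-month contact could have taken place. At stake are the clarity and reproducibility of supportive, secondary and tertiary mortality results.

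**Working it through.** **Primary calculation, for reference.** The point rests on no power figure. The stated power of about 80% (SAP 2.3: 400 per arm, 24% vs 16%, two-sided 5%) does reproduce: z = (0.08 × √400 − 1.96 × √(2 × 0.20 × 0.80)) / √(0.24 × 0.76 + 0.16 × 0.84) = (1.600 − 1.109) / 0.563 = 0.873, which gives 80.9%.

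**Log-rank stratified by treatment.** In each stratum, at each death time with d deaths among N at risk, of whom N1 are on ART-123 (d1 of the deaths):

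- Score: U = Σ(d1 − d·N1/N). Variance: V = Σ d(N1/N)(1 − N1/N)(N − d)/(N − 1).
- ART-123 stratum: N1 = N and d1 = d, so every term of U and V is 0.
- Placebo stratum: N1 = 0 and d1 = 0, so every term is again 0.
- U²/V = 0/0, whatever the data.

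A simulated data set (400 per arm, 24% vs 16% at Day 28, 40 equal sites assumed) shows only that the other version works. Stratified by treatment, U = 0 and V = 0. Stratified by site, U = −24.9 and V = 41.6, so chi-square = 14.9.

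**Days against the protocol windows.**

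| Month | Window, days after first dose | SAP 4.3.1.1 | SAP 4.3.2.1 / 4.3.3.1 | Latter read as days since first dose | Latter read as Study Day (minus 1) |
|---|---|---|---|---|---|
| 3 | 87–93 | 90 | 87 | 87: lower edge | 86: 1 day early |
| 6 | 177–183 | 180 | 177 | 177: lower edge | 176: 1 day early |
| 12 | 357–363 | 360 | 350 | 350: 7 days early | 349: 8 days early |

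Days 90, 180 and 360 lie inside the windows on both readings (89, 179 and 359 if they are Study Days). The pattern that yields 87 and 177 would yield 360 − 3 = 357, not 350.

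**Size.** The documents give no late mortality. Assume that 5%, 10% or 20% of Day-28 survivors die by day 360 at a constant hazard, equal in both arms. Day-28 survivors: 400 × 0.76 + 400 × 0.84 = 640. Expected survivors at day t: 640 × (1 − q)^((t − 28)/332).

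| Interval | Expected deaths (q = 5 / 10 / 20%) | Percentage points of 800 |
|---|---|---|
| 87 to 90 | 0.29 / 0.60 / 1.24 | 0.04 / 0.07 / 0.15 |
| 350 to 357 | 0.66 / 1.28 / 2.42 | 0.08 / 0.16 / 0.30 |
| 350 to 360 | 0.94 / 1.83 / 3.45 | 0.12 / 0.23 / 0.43 |

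Effect on the between-arm difference at q = 20%, days 350 to 360: placebo 3.45 × 304/640 = 1.64 deaths of 400 (0.41 points); ART-123 3.45 × 336/640 = 1.81 of 400 (0.45 points). The difference between arms moves by about 0.04 points.

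**Precision of a month-3 difference, if one were added.** Half-width of the 95% CI = 1.96 × √(p1(1 − p1)/400 + p2(1 − p2)/400). This is 5.5 points at 24%/16% and 6.3 points at 34%/26% (assumed range, ignoring censoring).

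**The case against.** The strongest reply is that these are copy-edits. SAP 3.6.5 already specifies the all-follow-up log-rank correctly, and a test with zero variance cannot silently give a wrong answer. That stands, and it limits the severity. It does not remove the need to correct a prespecified analysis rule.

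Four stronger readings are tempting, and the documents do not support them:

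- **The paired Kaplan-Meier values must differ.** A Kaplan-Meier curve steps only at deaths. With 0.29 to 1.24 deaths expected between days 87 and 90, the chance of none is e^−0.29 = 75% down to e^−1.24 = 29%, and the two values would then be identical.
- **Reading at day 350 biases the 12-month result.** Deaths are dated, and survivors are censored when last known alive (SAP 4.3.1.1 and 4.3.2.1). A subject found alive in the 12-month window therefore informs day 350. The result is a valid estimate for a slightly earlier day.
- **Month-3 mortality, a secondary endpoint, has no between-arm test.** SAP 3.6.2 gives Kaplan-Meier rates at 3, 6 and 12 months and a log-rank test stratified by pooled site. Only a comparison confined to month 3 is absent. Nor does it follow that this log-rank mostly reflects later follow-up because 270 of 360 scheduled days come after day 90. Its information follows deaths. On the assumptions above, deaths after day 90 are 26 of 192, 52 of 224 or 102 of 288, that is 13%, 23% or 35%.
- **Listing study day 28 and mortality day 28 separately is a contradiction.** The footnote in SAP 3.6.3 explains the distinction: "Twenty-eight days after the start of treatment is Study Day 29". What remains unstated is which axis the long-term day numbers use.

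**Conclusion.** Two errors stand. First, the log-rank test in SAP 4.3.1.1 cannot be computed as written. This is algebra and needs no assumption, and SAP 3.6.2 and 3.6.5 show the intended stratum. Second, the SAP uses two sets of long-term days, and its day 350 follows from no rule in either document, on either reading of the axis.

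The numerical effect is small: at most about 0.4 percentage points at month 12 over both arms combined, under the assumed 5 to 20% late mortality, and very little on the between-arm difference if the late hazard is equal. A reader might infer that the efficacy conclusion is exposed. It is not: the primary Day 28 Cochran-Mantel-Haenszel test, its alpha and the sample size use none of these provisions. Severity is minor.

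**What to change.** 1. In SAP 4.3.1.1, change the stratification factor of the log-rank test from treatment to pooled site.
2. Use one set of long-term days in SAP 4.3.1.1, 4.3.2.1 and 4.3.3.1: either 87/177/357 (window opening) or 90/180/360 (nominal day). Label them as days since first dose, in line with SAP 3.3.
3. Correct 350 to match: 357 or 360.
4. Optional: in SAP 4.3.2.1, add the between-arm Kaplan-Meier difference with its 95% CI at the chosen month-3 day. That section gives only survival estimates and plots, and the log-rank in 3.6.2 covers all available follow-up.

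The cost is SAP wording and a few programming lines. The protocol and data collection do not change.

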#### **4.3.2 Secondary Efficacy Analyses**

##### **4.3.2.1 All-cause Mortality at Month 3**

The Kaplan-Meier method will be used to estimate the survival rate at month 3 (study day 87). Kaplan-Meier plots of survival time will be also provided. All long term follow up data at the time of analyses will be used to obtain month 3 Kaplan-Meier estimates. Subjects whose status is alive, or unknown will be censored at the last available date that the subject was known to be alive.

##### **4.3.2.2 Shock, Ventilator, Dialysis Free and Alive days**

Shock free, ventilator free, and dialysis free days will be analyzed using a stratified Wilcoxon test (Van Elteren test) with pooled site as the stratification factor. The number of event free and alive days is calculated as Alive Days – Event days. Alive Days are defined in [Section 3.6.3](#). Each summary table will display a summary for number of Alive Days, Event free Days, and Event free and Alive Days. These tables will also be produced by baseline Renal Replacement Therapy status.

Shock days is defined as the number of days on concomitant vasopressor medication as collected in the eCRF vasopressor medication log.

Ventilator days are defined as the number of days on assisted breathing as collected in the eCRF ventilation log.

Dialysis days is defined as the number of days on dialysis as collected in the eCRF dialysis log.

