15.2 Appendix B: Key Study Definitions

Major Bleeding Events

A Major Bleeding event is defined as any intracranial hemorrhage, any life-threatening bleeding, any bleeding event classified as serious by the Investigator (e.g., resulting in permanent morbidity), or any bleeding that required the administration of at least 1440 mL (typically 6 units) of packed red cells over two consecutive days.⁶

All major bleeding events must be collected, documented, and promptly reported as SAEs.

Appropriateness of Initial Antibiotic Therapy

The Investigator will review all culture data from the time of infection onset to determine whether there is a definite identification of a causal organism (i.e., culture from a normally sterile site such as blood or pleural fluid), a likely identification of a causal organism (i.e., culture of suspected pathogen from another site with additional support [e.g., sputum culture where the sputum had < 10 epithelial cells and > 25 WBC per field]), or no causative organism identified. The Investigator will also review initial antibiotic therapy and organism MIC data, to determine whether it was appropriate for the known or suspected causative organism. Such review may include calculations of AUC/MIC relationships based on doses and anticipated clearances.

Mechanical Ventilation

Mechanical ventilation is described for the purposes of this protocol as any kind of ventilation administered via an endotracheal tube or nasotracheal intubation. This applies to all modes of ventilation (VA, VC and PC). Pressure Support Ventilation (PSV) is permissible. Simple administration of supplemental oxygen is NOT considered to be mechanical ventilation.

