15.4 Appendix D: Organ Dysfunction Scale²²

The following organ dysfunction/failure assessment is based on the ARDSnet organ dysfunction scale. The subject will be assessed, using this scale, daily from Baseline through Day 28. If the subject is discharged from the hospital, no further daily assessments are required after hospital discharge except on Day 14 and Day 28.

The presence of organ dysfunction will be determined based on laboratory or clinical parameters, as follows:

1. Hepatic: Any day with a bilirubin greater than or equal to 2.0 mg/dL will be counted as a hepatic insufficiency day, consistent with the ARDSnet criteria and a Sequential Organ Failure Assessment (SOFA) score greater than or equal to 2.^{7,20}
2. Renal: Any day with a creatinine greater than or equal to 2.0 mg/dL is counted as a renal dysfunction day, consistent with the ARDSnet criteria and a SOFA score greater than or equal to 2.^{7,18} Assess hemofiltration or dialysis use.
3. Respiratory: Any day that mechanical ventilation was used (except during surgery) is counted as a respiratory failure day. Assess PaO₂/FiO₂ ratio.
4. Shock (cardiocirculatory): Any day when a vasopressor is used will be counted as a shock day. Vasopressors include any use of norepinephrine, epinephrine, phenylephrine or vasopressin, or any use of dopamine at a dose greater than (>) 5 µg/kg/min. If vasopressin is used, it must be given in conjunction with another vasopressor.

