#### **3.6.4 Organ Dysfunction and INR**

The percent of subjects with Organ Dysfunction (Hepatic, Renal, Respiratory and Shock) and subjects INR scores will be summarized with descriptive statistics at Baseline, Day 3, Day 7, 24 hours post last dose, Day 14 and Day 28. For the organ dysfunction summary, the denominator will be subjects alive on the given mortality day (24 hours post last dose will not be summarized) and the numerator will be limited to subjects in the denominator. Subjects will be counted as having an organ dysfunction at each timepoint based on the analysis visit window structure found in [Table 1](#) of this SAP (if any of the events listed below occur within these windows the subjects is classified as having the dysfunction at that visit). Additionally, shift from baseline dysfunction status to post baseline status at each timepoint will be summarized. Organ dysfunction is defined as

Hepatic Dysfunction: Central lab bilirubin greater than or equal to 2.0 mg/dL

Renal Dysfunction: Central lab creatinine greater than or equal to 2.0 mg/dL

Respiratory Dysfunction: Mechanical ventilation as indicated from the ventilation log.

Shock Dysfunction: Vasopressor used as indicated on the vasopressor CRF page.

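### The SAP's rules for shock days and ventilator days omit limits set in protocol Appendices B and D, so two secondary endpoints may be counted more broadly than the protocol defines.

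*SAP*

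**What the plan says.** Shock-free and ventilator-free days are two of the four secondary efficacy endpoints (Protocol Section 6; SAP 3.2). Each is alive days minus event days, tested with a van Elteren test stratified by pooled site (SAP 3.6.3 and 4.3.2.2).

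**Shock.** SAP 4.3.2.2: "Shock days is defined as the number of days on concomitant vasopressor medication as collected in the eCRF vasopressor medication log". SAP 3.6.4 is equally open for the organ-dysfunction summary: any vasopressor on the CRF page marks the subject as in shock. Protocol Appendix D begins with a rule of the same breadth, "Any day when a vasopressor is used will be counted as a shock day", and then qualifies it. It names norepinephrine, epinephrine, phenylephrine and vasopressin, adds "any use of dopamine at a dose greater than" 5 µg/kg/min, and ends: "If vasopressin is used, it must be given in conjunction with another vasopressor".

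**Ventilation.** SAP 4.3.2.2: "Ventilator days are defined as the number of days on assisted breathing as collected in the eCRF ventilation log". SAP 3.6.4 describes the same log differently: "Respiratory Dysfunction: Mechanical ventilation as indicated from the ventilation log". Protocol Appendix B defines mechanical ventilation as "any kind of ventilation administered via an endotracheal tube or nasotracheal intubation" and rules out simple supplemental oxygen. Appendix D adds a surgery exception: "Any day that mechanical ventilation was used (except during surgery) is counted as a respiratory failure day".

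**The concern.** A programmer working from SAP 4.3.2.2 would count every day with an entry in the vasopressor log or the ventilation log. Nothing in that section leads to Appendix B or D. If the logs hold low-dose dopamine, or ventilation only for an operation, those days would be subtracted as organ-failure days although the protocol does not count them. Vasopressin given alone is a further case, depending on how Appendix D is read. Breathing support without a tube is another, depending on what the ventilation log records.

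Such days are foreseeable. Protocol Section 3 plans for major surgery during dosing. Section 2.6.1 has separate timing rules for patients who receive vasopressors or ventilation during surgery, and its shock criterion carries the same dopamine and vasopressin conditions as Appendix D.

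What is at stake is the definition of two endpoints that serve the organ-dysfunction objective. If the choice is left until treatment codes are known, one dataset can yield two different sets of free days.

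**Working it through.** The documents give no power, sample size or expected value for shock-free or ventilator-free days, so there is no figure of the plan's to reproduce. The check is a comparison of texts, followed by the size per subject.

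**Step 1. Limits in the protocol and whether the SAP carries them.**

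| Limit | Protocol | SAP 4.3.2.2 | SAP 3.6.4 |
|---|---|---|---|
| Named vasopressor agents | Appendix D | absent | absent |
| Dopamine only above 5 µg/kg/min | Appendix D | absent | absent |
| Vasopressin only with another agent | Appendix D (wording conflicts, see step 2) | absent | absent |
| Ventilation through a tube | Appendix B | absent (assisted breathing) | implied by the term mechanical ventilation |
| Ventilation during surgery excepted | Appendix D | absent | absent |

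The shock half is the firmer one, because Appendix D defines a shock day by that name and no SAP section restores its limits. On ventilation the SAP disagrees with itself about the tube requirement and is silent about surgery.

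**Step 2. Appendix D's own wording.** Appendix D puts vasopressin in the list of agents of which any use counts, and the next sentence makes it conditional on a second vasopressor. A day on vasopressin alone is a shock day under the first sentence and not under the second. The agent list is also introduced as what vasopressors include, so it is not clear that the list is closed. The dopamine limit has no such ambiguity.

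**Step 3. Size per subject.** From SAP 4.3.2.2:

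free days = alive days − event days.

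For a subject alive throughout, alive days = 28. Let q be the qualifying event days and x the logged days that do not qualify. Then

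- protocol count = 28 − q
- literal SAP count = 28 − q − x
- difference = −x

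The values of q and x below are assumed for illustration.

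| Endpoint | q | x | Protocol count | Literal SAP count |
|---|---|---|---|---|
| Shock-free | 4 | 0, 1, 2, 3 | 28 − 4 = 24 | 24, 23, 22, 21 |
| Ventilator-free | 6 | 0, 1, 3, 5 | 28 − 6 = 22 | 22, 21, 19, 17 |

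The gap is one free day per non-qualifying logged day. It is zero when x = 0, which is the case for every subject if the logs accept only qualifying use.

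**Step 4. Size in the trial.** The shift in an arm's mean is the share of subjects affected times their average x. The documents give neither quantity, overall or by arm, so neither the shift in the mean nor any change in the van Elteren result can be computed.

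**The case against.** The strongest reply is that the logs may already be filtered. Appendix D says subjects are assessed on its scale daily from baseline to Day 28, and the visit lists in Protocol Sections 5.3 to 5.15 have sites complete assessments of shock, ventilator and dialysis. Sites may therefore apply Appendix D when they enter data. This is plausible and cannot be excluded, because the eCRF and its completion rules are not in the documents. Nor is it shown. At baseline, sites record the dose for any subject on dopamine (Protocol Section 5.3) with no threshold, which hints at broader capture without proving it.

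Three stronger readings are tempting, and the documents do not support them.

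- A reader might infer that the two endpoints do measure something other than what the protocol defines. That depends on the unseen logs.
- A reader might infer that non-invasive support after extubation will count as ventilator days. SAP 3.6.4 reads the same log as mechanical ventilation, a term the protocol ties to intubation, so assisted breathing may only be loose wording. The missing surgery exception is not explained in this way.
- A reader might infer that the SAP cites the wrong protocol section when SAP 3.2 refers to Section 5.15. The same reference follows Day 28 in the INR endpoint, so it is best read as defining Day 28.

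It is also fair to say that Protocol Section 6 does not expressly tie the free-day endpoints to Appendix D, and that the surgery exception is written for a respiratory failure day, not a ventilator day. The link is nevertheless close: the endpoints are presented as measures of organ-dysfunction resolution through Day 28, and Appendix D is the protocol's daily organ-dysfunction scale for that period.

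**Conclusion.** The concern holds in a limited form. The SAP's written rules are broader than the protocol's for shock days (4.3.2.2 and 3.6.4) and for ventilator days (4.3.2.2), and the surgery exception is missing from the SAP altogether. Shock-free and ventilator-free days may therefore be counted more broadly than the protocol defines, at a cost of one free day per non-qualifying logged day and zero if the logs are pre-filtered.

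This assumes that Appendices B and D are meant to govern these endpoints and that the logs can hold non-qualifying entries. The first is strongly suggested, and the second is unknown.

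A reader might go on to infer a bias between arms. The documents give no ground for that: the trial is double-blind, the same counting rule applies to both arms, and nothing points to differential miscounting. The primary mortality analysis is unaffected. SAP 3.6.3 says the event-free-day tests are unpowered and not adjusted for multiplicity. The point concerns an endpoint definition that should be settled before unblinding and does not threaten the trial's main conclusion.

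**What to change.** Before the Day 28 database lock, at which SAP 2.5 has the sponsor unblinded:

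1. Reconcile SAP 4.3.2.2 and 3.6.4 with protocol Appendices B and D. This includes settling Appendix D's two vasopressin sentences and stating whether its agent list is closed.
2. Define a shock day in both SAP sections as a day with a vasopressor-log entry that meets the reconciled definition.
3. In SAP 4.3.2.2, replace assisted breathing with mechanical ventilation as defined in Appendix B. In both sections, handle surgery-only ventilation as Appendix D states.
4. If the eCRF already restricts the logs to qualifying use, say so in one sentence. That closes the point.

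The cost is SAP text and a filter in the derivation. Agent should be available, since SAP 4.2.7.3 tabulates vasopressors by type, and surgeries are recorded throughout the visit schedule. The drawback is that dopamine dose after baseline and tube type may not be in the logs: Protocol Section 5.3 asks for dopamine dose at baseline, but the later visit lists do not mention vasopressor dose. If a field is missing, the SAP should state which limit cannot be applied and report this as a deviation from the protocol definition.
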